6.5. Agent Accountability

Atorvastatin or placebo pills

Each participating NCORP and Alliance site will maintain a careful record of the inventory and disposition of the study agents received (atorvastatin or placebo pills) using the NCI Drug Accountability Record Form (DARF). This will include adequate records of receipt, dispensing, quantities, dates and final disposition of study agent.

ProHance®: Each participating MRI NCORP site will maintain a careful record of the inventory and disposition of the ProHance® received using the NCI Drug Accountability Record Form (DARF) or drug accountability form used at site. This will include adequate records of receipt, dispensing, quantities, dates and final disposition of the ProHance®. All remaining and or expired ProHance® must be disposed of according to site institutional policy. The site is responsible for maintaining the drug accountability record.

Each participating MRI NCORP site will maintain a careful record of the inventory and disposition of any sedative medication given to the patient according to institutional policy.

6.6 Packaging and Labels

Summary

The study will remain open approximately 5 years or until all 278 patients have been accrued and can complete the study. Biologics, Inc. will send to the participating site the 24-month supply for each patient randomized to the study, except for those patients who may be extending to within 27 months from the start of study. For these patients, Biologics may ship directly to patients.

Packaging

- All study drugs will include a patient specific label adhered to the bottles. Biologics will place the bottles in a Ziploc bag and include a patient specific label on the outside. Biologics will also include the study number on the label to avoid confusion at the sites.
- Each shipment includes a label on the Ziploc bags with the following information (as needed):
- The Study Number
- The Patient study ID number
- The Patient's name or initials
- The number of capsules
- Administration instructions: Take one tablet daily by mouth Drug identification (Atorvastatin 40mg OR Placebo)
- Expiration Date
- Dosing instructions (Administer as Directed per Protocol)
- Storage instructions ("Store at controlled room temperature, 20-25°C (68-77°F)")
- Date dispensed
- IND caution statement and/or local regulatory statements
- Emergency contact instructions

For all drug shipments from Biologics, Inc., a packing slip will be enclosed that includes the date and quantity of drug provided patient name/initials, study ID number, drug identification and expiration date.

Biologics, Inc. will process and ship "same day" of patient randomization if received before 5:00 p.m. EST Monday through Friday. Orders received after 5:00 pm EST Monday through Friday will be processed and shipped the next business morning.

All drug orders are shipped via *FedEx for Priority Overnight* delivery. Study drug is shipped in boxes designed to maintain temperature stability.

Once study drug is received at the clinical trial site, the designated site coordinator validates contents of package match information provided on packing slip with study medication received. The inventory and disposition of atorvastatin or placebo pills must be recorded using the NCI Drug Accountability Record Form (DARF).

ProHance® will be supplied by Bracco Diagnostics Inc. ProHance® is not dispensed as a patient specific medication; it is shipped in bulk to each individual site with appropriate manufacturing labeling and directions.

6.7. Storage

Atorvastatin pills are supplied as 40mg pills in 90 count bottles and stored at 20-25°C (68-77°F). ProHance® will be stored according to Bracco Diagnostics Inc. package insert.

6.8. Registration Process

All patient enrollments for Wake and non-Wake sites will go through the Wake Forest NCORP Research Base (see Section 6.8.2). NCORP sites can request membership through the Wake Forest NCORP Research Base.

6.8.1 Non-Wake sites can register through CTSU.

CTSU Registration Procedures for Wake and non-Wake NCORP Sites:

Cancer Therapy Evaluation Program Investigator Registration Procedures

Food and Drug Administration (FDA) regulations and National Cancer Institute (NCI) policy require all individuals contributing to NCI-sponsored trials to register and to renew their registration annually. To register, all individuals must obtain a Cancer Therapy Evaluation Program (CTEP) Identity and Access Management (IAM) account (<https://ctepcore.nci.nih.gov/iam>). In addition, persons with a registration type of Investigator (IVR), Non-Physician Investigator (NPIVR), or Associate Plus (AP) (i.e., clinical site staff requiring write access to OPEN, RAVE, or acting as a primary site contact) must complete their annual registration using CTEP's web-based Registration and Credential Repository (RCR) (<https://ctepcore.nci.nih.gov/rcr>).

RCR utilizes five person registration types.

- IVR — MD, DO, or international equivalent;
- NPIVR — advanced practice providers (e.g., NP or PA) or graduate level researchers (e.g., PhD);
- AP — clinical site staff (e.g., RN or CRA) with data entry access to CTSU applications (e.g., Roster Update Management System (RUMS), OPEN, Rave,);
- Associate (A) — other clinical site staff involved in the conduct of NCI-sponsored trials; and
- Associate Basic (AB) — individuals (e.g., pharmaceutical company employees) with limited access to NCI-supported systems.

RCR requires the following registration documents:

Documentation Required	IVR	NPIVR	AP	A	AB
FDA Form 1572	✓	✓			
Financial Disclosure Form	✓	✓	✓		
NCI Biosketch (education, training, employment, license, and certification)	✓	✓	✓		
GCP training	✓	✓	✓		
Agent Shipment Form (if applicable)	✓				
CV (optional)	✓	✓	✓		

An active CTEP-IAM user account and appropriate RCR registration is required to access all CTEP and Cancer Trials Support Unit (CTSU) websites and applications. In addition, IVRs and NPIVRs must list all clinical practice sites and IRBs covering their practice sites on the FDA Form 1572 in RCR to allow the following:

- Addition to a site roster;
- Assign the treating, credit, consenting, or drug shipment (IVR only) tasks in OPEN;
- Act as the site-protocol Principal Investigator PI on the IRB approval; and
- Assign the Clinical Investigator (CI) role on the Delegation of Tasks Log (DTL).

In addition, all investigators act as the Site-Protocol PI, consenting/treating/drug shipment, or as the CI on the DTL must be rostered at the enrolling site with a participating organization (i.e., Alliance).

Additional information can be found on the CTEP website at <https://ctep.cancer.gov/investigatorResources/default.htm>. For questions, please contact the **RCR Help Desk** by email at [contact].

Cancer Trials Support Unit Registration Procedures:

This study is supported by the NCI CTSU

IRB Approval:

For CTEP and Division of Cancer Prevention (DCP) studies open to the National Clinical Trials Network (NCTN) and NCI Community Oncology Research Program (NCORP) Research Bases after March 1, 2019, all U.S.-based sites must be members of the NCI Central Institutional Review Board (NCI CIRB). In addition, U.S.-based sites must accept the NCI CIRB review to activate new studies at the site after March 1, 2019. Local IRB review will continue to be accepted for studies that are not reviewed by the CIRB, or if the study was previously open at the site under the local IRB. International sites should continue to submit Research Ethics Board (REB) approval to the CTSU Regulatory Office following country-specific regulations.

Sites using their local IRB or REB, must submit their approval to the CTSU Regulatory Office using the Regulatory Submission Portal located in the Regulatory section of the CTSU website. Acceptable documentation of local IRB/REB approval includes:

- Local IRB documentation;
- IRB-signed CTSU IRB Certification Form; and/or

- Protocol of Human Subjects Assurance Identification/IRB Certification/Declaration of Exemption Form.

In addition, the Site-Protocol Principal Investigator (PI) (i.e. the investigator on the IRB/REB approval) must meet the following criteria to complete processing of the IRB/REB approval record:

- Holds an Active CTEP status;
- Rostered at the site on the IRB/REB approval (*applies to US and Canadian sites only*) and on at least one participating roster;
- If using NCI CIRB, rostered on the NCI CIRB Signatory record;
- Includes the IRB number of the IRB providing approval in the Form FDA 1572 in the RCR profile; and
- Holds the appropriate CTEP registration type for the protocol.

Additional Requirements

Additional requirements to obtain an approved site registration status include:

- An active Federal Wide Assurance (FWA) number.
- An active roster affiliation with the Lead Protocol Organization (LPO) or a Participating Organization (PO); and
- Compliance with all protocol-specific requirements (PSRs).

Downloading Site Registration Documents:

Download the site registration forms from the protocol-specific page located on the CTSU members' website. Permission to view and download this protocol and its supporting documents is restricted based on person and site roster assignment. To participate, the institution and its associated investigators and staff must be associated with the LPO or a PO on the protocol.

- Log on to the CTSU members' website <https://www.ctsu.org> using your CTEP-IAM username and password;
- Click on the Protocols tab in the upper left of your screen
 - Enter the protocol number in the search field at the top of the protocol tree, or
 - Click on the By Lead Organization folder to expand, then select [Corresponding Organization], and protocol number [NCI Protocol #];

Protocol Specific Requirements for WF- 98213 Site Registration:

- CTSU IRB Certification (for sites not participating via the NCI CIRB)
- CTSU IRB/Regulatory Approval Transmittal Sheet (for sites not participating via the NCI CIRB)
- ***See Section 8 for protocol specific training requirements. This must be completed prior to enrollment.***

Submitting Regulatory Documents:

Submit required forms and documents to the CTSU Regulatory Office via the Regulatory Submission Portal on the CTSU website.

To access the Regulatory Submission Portal log on to the CTSU members' website →
Regulatory →Regulatory Submission

Institutions with patients waiting that are unable to use the Regulatory Submission Portal should alert the CTSU Regulatory Office immediately at [name] in order to receive further instruction and support.

Checking Your Site's Registration Status:

You can verify your site's registration status on the members' side of the CTSU website.

- Log on to the CTSU members' website;
- Click on *Regulatory* at the top of your screen;
- Click on *Site Registration*;
- Enter your 5-character CTEP Institution Code and click on Go.

Note: The status shown only reflects institutional compliance with site registration requirements as outlined above. It does not reflect compliance with protocol requirements for individuals participating on the protocol or the enrolling investigator's status with the NCI or their affiliated networks.

6.8.2 Online Patient Enrollment Procedures for Sites (Wake and non-Wake sites)

Do Not Enroll Patients Through "OPEN"

IRB letter of approval and an IRB approved consent form must be received by the Research Base Protocol Information Office – Attn: Site Coordinator prior to patient enrollment. [contact]. An "Eligibility Checklist / Enrollment Form" will be used to complete the on-line enrollment.

Online Enrollment

Log on to the Wake Forest NCORP Research Base enrollment web site at <https://ccrbis.phs.wakehealth.edu>. Enter your user name and password (which may be obtained by contacting [name] at [contact] In the 'Patient Enrollment and Protocol Information' table, click the 'Register Patient/Patient Info', with the corresponding protocol number found in the drop down box to the right. Fill in the eligibility criteria forms using the drop down boxes. If further information is needed by Biologics or Data Management, they will contact you. Once the patient information has been entered online print a copy of the eligibility checklist/enrollment form for your records. Press the submit button, a confirmation page will appear. Print this confirmation sheet for your records. The Wake Forest NCORP On-line Protocol Enrollment/Eligibility form, initial flow sheet, signed consent, should be faxed to [contact] or mailed to Data Management:

Wake Forest NCORP Research Base
Data Management Center
Wake Forest Baptist Medical Center
[name]
[name]
[name]

These forms should be retained in the patient's study file. These forms will be evaluated during an institutional NCI/Wake Forest NCORP Research Base site member audit.

If you have questions related to the enrollment process or require assistance with enrollment, please contact the Wake Forest NCORP Research Base DMC between 8:30am and 4:00pm EST, Monday through Friday at [contact] or [name].

6.8.3 Randomization Process

See Section 12.1

6.9. Unblinding Methods

In the event a patient on this study develops a toxicity (adverse event or severe adverse event) for which the patient's physician or other health care professional feels that it is in the patient's best interest to know what drug they are taking (active study drug or placebo), the following procedure should be followed:

- Step 1: The patient's physician or a designated health care professional should call the Wake Forest University Baptist Medical Center Physician Access Line at [contact] and ask that [name], Director of the WF NCORP Research Base, be contacted immediately either in his office, by pager, or at home. In the event [name] cannot be reached, the PAL operator should contact [name], Director, Symptom Treatment Protocols, in her office, by pager, or at home. If neither [name] nor [name] can be reached, the PAL operator should contact [name], Co-Investigator, in his office, by pager, or at home. If [name], [name] or [name] cannot be reached, the PAL operator should contact [name], Co-Investigator, in his office, by pager, or at home.
- Step 2: Once contact has been made, the patient's physician or health care professional should explain the reason for the request to unblind the treatment arm that the patient is on. If the Research Base representative feels that the toxicity (AE/SAE) is possibly, probably or definitely related to the study drug, then the next step will be followed.
- Step 3: The responsible Research Base representative will call the pharmacist @ Biologics, Inc. ([contact]). There is an "on-call" service provided 24 hours a day, seven days a week for the Chemical Drug Trials unblinding service. The Biologics pharmacist may contact the patients' physician and/or health care professional directly with the unblinding information. Written documentations of the unblinding process will be sent to the Research Base Principal Investigator by Biologics, Inc.
- Step 4: In the event that the patient's treatment is unblinded, that patient will be taken off study with no further study follow-up. Appropriate procedures for grading toxicities, assigning causality, and reporting severe adverse events (if applicable), should be followed. The event will be reviewed by the WF NCORP Safety and Toxicity Review Committee and reviewed by the NCORP Research Base Data Safety and Monitoring Board.

Record the details of the adverse event and/or unblinding in the site source documentation and complete appropriate AE forms.

Unblinding Study Participants at Study Completion

Study participants may be unblinded at the conclusion of the study if **all** patient specific data for the requesting site are completed and submitted to the Data Management Center (DMC) and all of the primary study outcomes have been determined and the final data set is cleaned and prepared for analysis. Site members can obtain unblinding information by sending an email request to the WF NCORP Administrator or Data Management Supervisor with a list of PID #s. After confirming with the DMC that patient specific data for all patients at the requesting site have been received, completed and entered into the RB database, the Research Pharmacy will be notified. An email from the Research Pharmacy containing the unblinding information will be sent directly to the requesting site.

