4.2 Exclusion Criteria

- 4.2.1 Atherosclerotic cardiovascular disease (ASCVD) defined by history of acute coronary syndromes, MI, stable or unstable angina, coronary or other arterial revascularization, stroke, TIA, or peripheral arterial disease presumed to be of atherosclerotic origin.
- 4.2.2 40 to 75 years of age with diabetes per ACC/AHA 2013 Guidelines
- 4.2.3 Significant ventricular arrhythmias (>20 PVCs/min due to gating difficulty) atrial fibrillation with uncontrolled ventricular response
- 4.2.4 Current use of statin therapy
- 4.2.5 Current or history of hepatic dysfunction
- 4.2.6 Uncontrolled hypothyroidism
- 4.2.7 Recent extended history of constant-recurrent substance abuse or another medical condition that might compromise safety or the successful completion of the study.
- 4.2.8 Patients with ferromagnetic cerebral aneurysm clips or other intraorbital/intracranial metal; pacemakers, defibrillators, functioning neurostimulator devices or other implanted electronic devices.
- 4.2.9 Current use of the following CYP 3A4 inhibitors are not allowed: Boceprevir, Clarithromycin, Cyclosporine (oral), Darunavir plus ritonavir, Fosamprenavir, Fosamprenavir plus ritonavir, Gemfibrozil, Grapefruit juice >1 liter per day, Itraconazole, Lopinavir plus ritonavir, Nelfinavir, Saquinavir plus ritonavir, Telaprevir, Tipranavir plus ritonavir

- 4.2.10 Current use of Rifampin and Digoxin
- 4.2.11 Unable to provide informed consent
- 4.2.12 Symptomatic Claustrophobia
- 4.2.13 Pregnant or breast feeding. Due to unknown risks and potential harm to the unborn fetus a negative serum pregnancy test within 10 days prior to enrollment is required in women with child-bearing potential. For this reason women of child-bearing potential must agree to use adequate contraception (hormonal or barrier method of birth control; abstinence (not having sex), oral contraceptives, intrauterine device (IUD), DeProvera, tubal ligation, or vasectomy of the partner (with confirmed negative sperm counts) in a monogamous relationship (same partner). An acceptable, although less reliable method involves the careful use of condoms and spermicidal foam or gel and/or cervical cap or sponge prior to study entry and for the duration of study participation. Should a woman become pregnant or suspect she is pregnant while participating in this study, she should inform her study physician immediately.

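### Section 6.9 lets a relatedness judgement stop a request to open the code, and states no route during the study for a pregnancy on study drug

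*Combined protocol and SAP*

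**What the plan says.** Section 6.9 (Unblinding Methods) opens with an entry condition: "In the event a patient on this study develops a toxicity (adverse event or severe adverse event". Within that condition, the ground for asking is that the physician or other health professional judges it to be in the patient's "best interest to know what drug they are taking (active study drug or placebo".

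The steps then run as follows.

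- **Step 1.** The requester telephones an access line, which works down a list of four Research Base or study roles.
- **Step 2.** The requester "should explain the reason for the request to unblind the treatment arm that the patient is on". The procedure continues on this condition: "If the Research Base representative feels that the toxicity (AE/SAE) is possibly, probably or definitely related to the study drug".
- **Step 3.** The Research Base representative, not the requester, calls the Biologics pharmacist, whose service runs around the clock. The pharmacist may give the allocation directly to the physician or the other health professional.
- **Step 4.** A patient whose code is opened leaves the study and is no longer followed.

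The second part of Section 6.9 covers unblinding at study completion. It requires, among other things, that "all of the primary study outcomes have been determined and the final data set is cleaned and prepared for analysis".

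On pregnancy, Section 4.2.13 cites possible harm to the fetus as the reason for the pregnancy test before enrollment, and adds: "Should a woman become pregnant or suspect she is pregnant while participating in this study, she should inform her study physician immediately". It does not mention the code.

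**The concern.** Emergency unblinding exists so that whoever is caring for a patient can learn the allocation when care depends on it. Section 6.9 recognises this in its opening sentence, then hands the decision to a second person who applies a different test. Need and causality are separate questions: an event may be unrelated to study drug while the patient's care still depends on knowing what was taken. Relatedness is also judged blind at that moment, and the allocation is part of the information that would help to settle it.

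Pregnancy shows the gap in the trigger. The protocol expects that it may happen and wants it reported to the study physician at once, but Section 6.9 is written only for toxicities. Stopping study drug limits further exposure. It does not tell the physician whether the patient has already been exposed to atorvastatin.

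At stake is the safety of individual patients, and the completeness of follow-up for anyone who is unblinded.

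**Working it through.** The plan states no figure on this point and no calculation applies. The check is to trace each path through Section 6.9 and set it beside the related sections.

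1. **Toxicity, request made, representative judges it at least possibly related.** Step 2 says that if the event "is possibly, probably or definitely related to the study drug, then the next step will be followed". Step 3 follows, the code is opened and Step 4 applies. This path is complete.
2. **Toxicity, request made, representative judges it unrelated.** The condition in Step 2 is not met. Section 6.9 has no branch for this case, no override by the requester and no direct access by the site to the pharmacist. As written, the request stops.
3. **Pregnancy without a toxicity.** The entry condition is not met, so Step 1 is not reached. The only other route stated is study completion, after outcomes are determined and the data set is cleaned.
4. **Pregnancy reported as an event.** The serious adverse event criteria in Section 10.1 name a birth defect but not pregnancy. Their catch-all lets an investigator report an event thought unusual or potentially serious. That rule governs reporting. If it did bring a pregnancy into Section 6.9, Step 2 would still ask whether study drug caused a toxicity, which is not the question that a pregnancy raises.

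**Who could be affected.** Table 2 in Section 4.3 plans 240 women among 278 participants (240/278 = 86%). Entry is from age 21 (Section 4.1.3) and dosing lasts 24 to 27 months (Section 5.1). The documents do not say how many of these women are of child-bearing potential, how many pregnancies are expected or how often a code request is expected, so no count can be derived.

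**Step 4 beside the rest of the plan.** Section 7.8 says that participants who come off study drug are still followed where possible, for safety and for endpoint data. Section 7.9 keeps even patients who start an open-label statin in the other parts of the trial. Section 12.3 puts all randomized patients in the primary comparison. Step 4 goes the other way and ends follow-up because the code was opened. Section 12.6 already allows for 78 dropouts (278 − 200), and each unblinded patient adds to the missing 24- to 27-month LVEF values. Any widening of access to the code therefore has to deal with Step 4 as well.

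**The case against.** The strongest reply is that the two tests do not contradict each other: the opening sentence says when to call, and Step 2 says what happens on the call. A central check protects the blind, and a bare possibility of relatedness is enough to pass it. This stands in part. A central check is a legitimate design choice and refusals may be few. It does not explain why the check should be causality rather than need, or why the unrelated case is left without an outcome.

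A second reply is that pregnancy can be handled without the code. Section 7.8 allows study drug to be stopped for a medical contraindication, and Section 5.6.2.3 gives a contact for medication issues. That is true of stopping the drug, but neither section gives access to the allocation. It is also fair that the wording on fetal harm in Section 4.2.13 is not clearly about atorvastatin, because Section 7.2 uses similar wording for pregnancy tests before MRI.

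A third reply concerns cost: under Step 4, more unblinding means more patients lost to follow-up. This stands in full and shapes the fix.

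A reader might also infer more than the text supports:

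- **That requests will be refused.** Section 6.9 never says so. Refusal follows only from a condition with no alternative branch.
- **That the representative is far away and has not seen the patient.** The text says only that contact is by telephone, and for some sites the representative may be close at hand.
- **That pregnancy can never reach the code.** The text reviewed contains no Section 6.4 or 7.6 and no consent form, so the finding is that no route is stated, not that none exists.
- **That the wait until study completion measures the harm.** It shows only that this route comes too late to help with a pregnancy.

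**Conclusion.** The point holds in this form. A request grounded in the patient's interest can stop at Step 2 on a relatedness judgement, with no stated outcome and no override. Pregnancy on study drug has no stated route to the allocation before study completion. This is more than missing detail, because a written rule can block a safety request.

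The size is small in patients and cannot be quantified from the documents. It may matter a great deal to the individual concerned, and it does not threaten the primary analysis. The conclusion rests on reading Step 2 literally and on the text available. It would weaken if the consent form or another section not seen here gives a separate route.

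**What to change.** Amend Section 6.9 in four places and reconcile a fifth.

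1. Make one test govern Step 3: a documented statement by the patient's physician or other health professional that the allocation is needed for the patient.
2. Have the Research Base representative record an opinion on relatedness, without a veto.
3. Name pregnancy on study drug in the trigger, alongside toxicity, and cross-refer to Section 4.2.13.
4. Keep disclosure available to the requesting professional, as Step 3 does now. Restricting it to the treating physician would narrow present access.
5. Reconcile Step 4 with Section 7.8 and the intent-to-treat analysis in Section 12.3, so that opening the code does not by itself end outcome and safety follow-up.

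The cost is a short protocol amendment and possibly a few more individual unblindings, in a number that the documents do not allow one to estimate. If Step 4 stays as it is, the cost also includes the later LVEF and safety data of each such patient. Items 1 to 4 should therefore not be adopted without item 5. The change concerns access to the code and continued data collection. It proposes no treatment or stopping rule.
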